# 1 Protocol Synopsis

PROTOCOL TITLE: Phase II Study of response adapted therapy using single agent lenalidomide in older adults with newly diagnosed standard risk multiple myeloma.

PROTOCOL NUMBER:	MCC16018			
IRB APPROVAL DATE OF	12/08/2009			
PROTOCOL:				
STUDY DRUG(s):	Lenalidomide (Revlimid®)			
	Prednisone			
	Dexamethasone (Decadron)			
INDICATION:	Newly Diagnosed (standard risk) Multiple Myeloma			
	with Active Disease			
STUDY PHASE:	2			

## STUDY OBJECTIVES:

## **Primary:**

1- To estimate the efficacy of a response adapted approach of treatment of older adults with standard risk multiple myeloma

## **Secondary:**

 To evaluate the efficacy of single agent lenalidomide in patients with standard risk multiple myeloma Page 5 of 86 Confidential

2. To evaluate the safety and efficacy of the combination of lenalidomide and prednisone in non responders to single agent lenalidomide

3. To evaluate markers of lenalidomide induced tumor immunity in patients treated with single agent lenalidomide

#### STUDY DESIGN:

This is a multi-center, single-arm, phase 2, open-label study of lenalidomide [Revlimid® (R)] based therapy in older adults with standard risk multiple myeloma. After enrollment patients will receive single agent lenalidomide. Responders (minimal response or better) after 2 cycles will continue present therapy until disease progression or intolerable toxicity. Patients with stable disease after 2 cycles will receive prednisone (100 mg orally on days 1 to 5 of each cycles) in addition to lenalidomide. Patients with evidence of disease progression after 2 cycles of single agent lenalidomide will receive low dose dexamethasone (40 mg weekly) in addition to lenalidomide. Patients not receiving low dose dexamethasone and with disease progression at any time during the study will be eligible to receive low dose dexamethasone in combination with lenalidomide. Patients on lenalidomide and low dose dexamethasone who experience disease progression at any time during the study will be taken off study and treated with alternative therapies..

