## STUDY ENDPOINTS

#### **Primary:**

1- The 12-month progression free survival (PFS) of older adults with mildly symptomatic multiple myeloma treated on this response adapted approach (i.e. time from lenalidomide start to failure of lenalidomide and low dose dexamethasone)

Page 6 of 86 Confidential

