## 5. Study Endpoints

## **Primary:**

1- The 12-month progression free survival (PFS) of older adults with mildly symptomatic multiple myeloma treated on this response adapted approach (i.e. time from start of lenalidomide to failure of lenalidomide and low dose dexamethasone)

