In addition, this study will evaluate the role of an alternative corticosteroid in combination with lenalidomide. Prednisone is known to be a better tolerated corticosteroid than dexamethasone without a compromise in the efficacy. This was seen in a recent report of a clinical trial by the national cancer institute of Canada study comparing melphalan prednisone to melphalan dexamethasone (grade 3 and 4 infections; 9 versus 15%, p=0.03)[18]. In addition, the intergroupe francais du myelome (IFM) had noted similar finding in older adults with newly diagnosed myeloma randomized to melphalan prednisone or dexamethasone based induction[19]. Both trials did not note a superiority of dexamethasone based induction to the prednisone based induction.

Page 26 of 86 Confidential

The primary endpoint of this study will be the progression free survival of patients treated with this response adapted approach. This is defined as the time from enrollment to failure of lenalidomide and low dose dexamethasone. Outcomes of this cohort of patients treated with this response adapted approach would be compared to patients treated with lenalidomide and low dose dexamethasone. If this response adapted approach results in similar or improved outcomes compared to therapy with lenalidomide and low dose dexamethasone, this approach would be favored since it likely result in less toxicity by using an overall lower dosage of corticosteroid.

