# 8.1.5.2. Dose reduction steps for corticosteroids

For patients assigned to receive corticosteroids as part of the trial therapy, dose reduction steps for prednisone and dexamethasone should follow the guidelines in the following tables. Table 2 refers to dose levels for the corticosteroids used on this clinical trial: prednisone and dexamethasone. Table 3 suggests dose reduction schema dictated by specific adverse events.

Table 3: Dose Reduction Steps for Dexamethasone and / or Prednisone

Starting Dose	Dose level –1	Dose Level -2	Dose Level -3
40 mg daily on days 1	20 mg daily on days 1	10 mg daily on days 1	Discontinue
– 4 every 28 days	– 4 every 28 days	– 4 every 28 days	
	Dose level -1a		

Page 44 of 86 Confidential

	40 mg daily on days		
	1, 2, and 3 followed		
	by 20 mg on day 4		
	followed by 12 mg on		
	day 5 followed by 8		
	mg on day 6		
Prednisone 100 mg	50 mg PO days 1-5 of	25 mg PO days 1-5 of	Discontinue
PO days 1-5 every 28	a 28 day cycle	a 28 day cycle	
days			

Page 45 of 86 Confidential

Table 3: Dose Modification Guidelines for corticosteroids (Dexamethasone and / or Prednisone)

CTCAE	ADVERSE EVENT	TREATMENT ADJUSTMENT
CATEGORY		
ADVERSE		
EVENT		
Gastrointestinal	Dyspepsia, gastric or duodenal	Treat with H2 blockers, sucralfate, or
	ulcer, gastritis	Omeprazole. If symptoms persist despite
	Grade 1-2	above measures, decrease corticosteroid
		dose by 2 dose levels permanently
	> Grade 3	Hold corticosteroids until symptoms are
		adequately controlled. Reduce by 2 dose
		levels along with concurrent therapy with
		H2 blockers, sucralfate, or omeprazole. If
		symptoms persist despite above measures,
		discontinue corticosteroids and do not
		resume.
	Acute pancreatitis	Discontinue corticosteroids and do not
		resume
Cardiovascular	Edema	Diuretics as needed, and decrease
	> Grade 3	corticosteroids dose by 1 dose level; if
		edema persists despite above measures

Page 46 of 86 Confidential

		decrease dose by 2 dose levels from the
		initial dose; discontinue corticosteroids and
		do not resume if symptoms persist despite
		reduction.
Neurology	Confusion or Mood alteration	Hold corticosteroids until symptoms
	> Grade 2 (interfering with	resolve to ≤ grade1. Reduce dose by 2 dose
	function	levels from current dose.
	+/- interfering with activities of	If symptoms persist despite above
	daily	measures, discontinue corticosteroids and
	living)	do not resume.
Musculoskeletal	Muscle weakness	Decrease corticosteroids dose by 1 dose

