#### **8.1.7.** Discontinuation from treatment

The following events are considered sufficient reasons for discontinuing a subject from study drug:

- Subject declines further study participation.
- Adverse event(s) (AEs) that, in the judgment of the Investigator, may cause severe or permanent harm or which rule out continuation of study drug.

Page 48 of 86 Confidential

- Major violation of the study protocol.
- Progression of disease/unsatisfactory therapeutic effect

Page 49 of 86 Confidential

- Death
- Pregnancy or a positive pregnancy test
- Discontinuation of lenalidomide for any reason
- Subject lost to follow-up
- If for any other reason, must be specified in the data collection system.

Study Closure

Reasons for discontinuation should be recorded in the data collection system and in the subject's medical records.

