#### **12.2.** Efficacy evaluation

#### 12.2.1 Primary efficacy analysis

Progression free survival (PFS) is defined as the time from start of lenalidomide monotherapy to the first occurrence of disease progression or death on study from any cause, whichever occurs earlier. All treated patients will be included in efficacy endpoint analysis. Those patients who are treated on this trial but have not had a relevant event at the time of last follow-up will be included in the analyses of these endpoints as censored observations.

Page 66 of 86 Confidential

The primary endpoint is the point estimate of the 12-month PFS rate for the overall response adaptive approach. Number and percentage of patients who survived greater or equal to 365 days without disease progression will be summarized. The 95% confidence interval will be calculated using the exact binominal method. The PFS curves will be estimated by the Kaplan-Meier method. Median and its 95% confidence intervals will be estimated.

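### After a permanent corticosteroid stop with lenalidomide continuing, the treatment rules at progression conflict, and under the failure-of-Ld event that progression may be missed or counted late

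*Combined protocol and SAP*

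**What the plan says.** **Treatment at progression.** The Study Design part of the Synopsis has two branches. The first is "Patients not receiving low dose dexamethasone and with disease progression at any time during the study will be eligible to receive low dose dexamethasone". The second is "Patients on lenalidomide and low dose dexamethasone who experience disease progression at any time during the study will be taken off study". Section 6.1 has dexamethasone added at progression and names no exception.

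**Permanent corticosteroid stops.** The dose modification table for corticosteroids in Section 8.1.5.2 covers both dexamethasone and prednisone. For acute pancreatitis, and for gastrointestinal, edema, mood or muscle weakness toxicity that persists despite the listed measures, its instruction is to "discontinue corticosteroids and do not" resume them.

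**Ending study drug.** Section 8.1.7 lists "Discontinuation of lenalidomide for any reason". It also lists progression, without tying it to Ld. It does not list stopping the corticosteroid alone.

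**Primary event.** Four places define it:
- Synopsis: "time from lenalidomide start to failure of lenalidomide and low dose dexamethasone".
- Section 5: "time from start of lenalidomide to failure of lenalidomide and low dose dexamethasone".
- Section 6.2: "This is defined as the time from enrollment to failure of lenalidomide and low dose dexamethasone".
- Section 12.2.1: "first occurrence of disease progression or death on study from any cause, whichever occurs earlier", with patients who have had no relevant event at last follow-up censored.

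The first three rest on failure of Ld and do not define failure.

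**The concern.** The two Synopsis branches do not distinguish a patient who has never had dexamethasone from one whose dexamethasone was permanently stopped. Both are, literally, not receiving it. Two things follow.

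First, the treatment text conflicts for patients with serious steroid toxicity: one place opens dexamethasone and another bars corticosteroids.

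Second, it is unclear whether such a patient's next progression is a failure of Ld, since the patient is then taking lenalidomide without dexamethasone. If it is not counted, a patient who could not tolerate the last step and then progressed may be recorded as progression-free at 12 months. That error favours the strategy, which Section 6.2 would prefer on grounds of lower toxicity if its outcomes are similar or better.

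**Working it through.** **1. Patient A: dexamethasone stopped.** The patient progresses, starts Ld, has dexamethasone permanently stopped under Section 8.1.5.2, stays on lenalidomide and progresses again.
- The off-study branch covers patients on Ld. Read literally, A is not on Ld.
- The other branch covers patients not receiving dexamethasone. Read literally, it makes A eligible, and Section 6.1 adds the drug.
- Section 8.1.5.2 says corticosteroids are not to be restarted.
- Section 8.1.7 would permit ending study drug at this progression but does not say how it is scored.

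**2. Patient B: prednisone stopped.** B takes lenalidomide plus prednisone, has the corticosteroid permanently stopped, stays on lenalidomide and progresses. The same treatment conflict arises, because the table covers corticosteroids as a class.

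**3. How A's second progression is scored.**

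| Definition | Result |
|---|---|
| Failure of Ld, read as progression while on Ld; dexamethasone not resumed | Not scored |
| Same reading; dexamethasone resumed | Scored late, at the next progression |
| Failure of Ld, read to include progression after dexamethasone was stopped | Scored on time |
| Section 12.2.1, first progression or death | Event already recorded before dexamethasone began |

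The last row follows because the Synopsis and Section 6.1 introduce dexamethasone only at progression. Any patient who received it per protocol already has a Section 12.2.1 event.

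**4. Direction.** Compared with scoring the second progression when it happens, omitting or delaying it can only raise the 12-month proportion or leave it unchanged. A late score changes that proportion only if it moves the event past day 365.

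**5. The plan's own figure.** Section 12.1 gives 60 evaluable patients, an assumed 85% and a 95% interval of 73.4–92.9%. Section 12.2.1 specifies the exact binomial method. With x = 0.85 × 60 = 51:
- lower limit = Beta quantile (0.025; x, n − x + 1) = Beta quantile (0.025; 51, 10) = 73.4%
- upper limit = Beta quantile (0.975; x + 1, n − x) = Beta quantile (0.975; 52, 9) = 92.9%

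The stated interval is reproduced.

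**6. Weight of each patient.** 1/60 = 1.7 percentage points. Suppose k of the 51 patients counted as event-free had in fact progressed by day 365 after a dexamethasone stop. The values of k are illustrative; the documents give none.

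| k | Patients event-free | Estimate | Exact 95% interval |
|---|---|---|---|
| 0 | 51/60 | 85.0% | 73.4–92.9% |
| 1 | 50/60 | 83.3% | 71.5–91.7% |
| 2 | 49/60 | 81.7% | 69.6–90.5% |
| 3 | 48/60 | 80.0% | 67.7–89.2% |

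From k = 2 the lower limit is below the roughly 70% that Section 12.1 cites for Ld.

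**The case against.** The strongest reply is Section 12.2.1. It is the primary analysis section, and under its event no later progression can be hidden. That is correct, and the endpoint concern falls away if that section governs. It does not settle the matter. Under it, every patient who moves to Ld has already failed, which contradicts the Synopsis and Sections 5 and 6.2. It also sits badly with the section's own statement that the rate describes the overall response adaptive approach.

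A reader might infer that such a patient is sent back to a barred drug and never has the primary event. The documents do not support either half in that form:
- The Synopsis makes the patient eligible; it does not order re-treatment. Section 6.1 is firmer, but the bar in Section 8.1.5.2 is more specific, and that section describes its table as suggesting reductions. Section 8.1.7 also allows study drug to end at progression. This is an unreconciled conflict, not an instruction to re-treat.
- Failure is undefined and can be read to include progression after dexamethasone was given and stopped. A patient who was re-treated would be scored late, not never.

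The lowest step of the dose-level table says only to discontinue and does not bar restarting. The clear conflict is therefore confined to the toxicities listed in the modification table.

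It is also fair that the sequence must be completed by day 365 to matter: first progression, Ld, permanent stop, second progression. Affected patients may be few. Section 12.1 sizes the trial for precision and sets no test against 70%, so crossing that figure changes interpretation, not a formal decision.

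**Conclusion.** The point holds in limited form. The Synopsis and Section 6.1 conflict with Section 8.1.5.2 for a patient who stays on lenalidomide after a permanent corticosteroid stop, whichever steroid it was. Under the event in the Synopsis and Sections 5 and 6.2, progression after dexamethasone was stopped may be missed or counted late, with upward bias in 12-month PFS. Under Section 12.2.1 it does not arise. Which case applies is undecided because the definitions disagree.

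The size is unknown beyond 1.7 points per affected patient at n = 60. A reader might attach a range by assuming that 15–25 of 60 patients reach Ld within 12 months, 10–20% of them stop dexamethasone for good, and 50–100% of those progress by day 365. That gives 15 × 0.10 × 0.5 = 0.75 to 25 × 0.20 × 1.0 = 5 patients, or 1.3 to 8.3 points. None of the three rates is in the documents, so this is not an estimate of the bias.

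**What to change.** 1. Use one primary event definition in Sections 1, 5, 6.2 and 12.2.1. If failure of the last step is the event, state that any progression or death after dexamethasone was first started counts, whether or not dexamethasone is still being taken. That sentence does not reach a patient who never starts dexamethasone, such as B, so the single definition should say how that patient is scored as well.
2. Reconcile the Synopsis and Section 6.1 with the corticosteroid table for patients whose corticosteroid was permanently stopped. The clinical team decides the rule, and the same wording should appear in each place.

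The cost is wording; no new data are needed, and the estimate may become slightly less favourable. Timing needs care. The rationale for Amendment 6 reports the last enrolment at this centre in 6/2013, so the 12-month window there had passed before the version dated 4/15/2016. A definition settled now should be dated and disclosed as a late clarification, with 12-month PFS reported under both definitions.

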## STUDY ENDPOINTS

#### **Primary:**

1- The 12-month progression free survival (PFS) of older adults with mildly symptomatic multiple myeloma treated on this response adapted approach (i.e. time from lenalidomide start to failure of lenalidomide and low dose dexamethasone)

Page 6 of 86 Confidential

## **Secondary:**

1- The response rate of older adults with mildly symptomatic multiple myeloma to single agent lenalidomide, lenalidomide prednisone and lenalidomide low dose dexamethasone in patients with suboptimal responses to lenalidomide monotherapy

- 2- The toxicity profile of these lenalidomide based combinations
- 3- The progression free survival of patients treated with single agent lenalidomide
- 4- The 1 year overall survival (OS) of older adults with mildly symptomatic multiple myeloma treated on this response adapted approach

## **Exploratory**

- 1-Measure a lenalidomide induced tumor specific immune response and correlate the tumor specific immune response with corticosteroid use, response to therapy and duration of response
- 2- To evaluate the impact of lenalidomide mono-therapy on expression of tumor suppression genes and cell cycle regulators

STUDY DURATION: Patients will receive study therapy until evidence of disease progression on lenalidomide and low dose dexamethasone, unacceptable toxicity or withdrawal of consent

**TOTAL SAMPLE SIZE:** approximately 30 patients enrolled at Moffitt and 30 patients enrolled in a parallel identical design study in multiple sites in South Korea.

**STUDY DRUG SUPPLIES:** Lenalidomide capsules will be supplied by Celgene Corporation at no charge through the RevAssist® program.

Commercial supplies of dexamethasone (Decadron®) and prednisone tablets will be utilized.

Commercial supplies of aspirin will be utilized.

Page 7 of 86 Confidential

#### **DOSING REGIMENS:**

- Oral Lenalidomide (R) will be administered every 28 days as follows:
  - 25 mg QD PO daily on Days 1-21 followed by 7 days rest (10 mg dose will be used for patients with a Creatinine clearance < 60 ml/min)
- Oral Prednisone (100 mg) will be administered on days 1 to 5 of every 28 days cycle in patients receiving combination lenalidomide and prednisone (LP).
- Oral dexamethasone (40 mg) will be administered once a week in patients receiving lenalidomide and low dose dexamethasone (Ld).

All subjects will also receive concomitant aspirin 81 mg PO daily. For patients who cannot tolerate aspirin, low molecular weight heparin or therapeutic doses of coumadin may be used in place of aspirin.

#### Rationale for Amendment 6

MCC16018 has enrolled 30 patients from 2/2010 to 6/2013. It has been closed to accrual since 10/2013 given it met its accrual target. Currently, six patients only continue on treatment, for now 2-4 years. We anticipate to final close the study as soon as a manuscript has been published. Of note, lenalidomide was approved by the FDA for newly diagnosed multiple myeloma patients in 2/2015. MCC16018 involves lenalidomide based therapy for newly diagnosed multiple myeloma and is thus currently considered standard of care (although that use was considered investigational at the time of initiation and completion of accrual of the study). Accordingly, we propose to collect more limited data pertaining to the current treatment of study subject as of 2/2016 until the final closure of the trial. Specifically, we will only plan to capture only serious adverse events (SAE), response and follow up data. Patients will continue on treatment and undergo standard of care monitoring which is at the discretion of the treating physician.

The changes made with this amendment will serve several purposes:

- 1- Decrease the burden on patients to comply with study requirement (for example, comply with study visit timeframe).
- 2- Decrease the number of deviations due to non-compliance with study requirements (such as missed 24h urine protein electrophoresis, laboratory testing outside the window).
- 3- Decrease the burden to the study team which would otherwise continue to collect additional data which will not aid in the overall interpretation of the study results (it is unlikely that a new toxicity to lenalidomide will be encountered in this study population that have been on this treatment for now 2-4 years on average)

Page 8 of 86 Confidential

# 2 Schedule of Study Assessments

Procedure	Screening/ Baseline (-28 Days)	Cycle 1 Day 1	Cycle 2 day 28	Every 4 Weeks (1 st 6 cycles)	Maintenance Every 3 months except where Indicated	Addition of Prednisone or Dexamethasone	2 months after the addition of dexamethasone	Off Study 
	ı		ı	1			T	
Informed consent	X	-	-	-	=	-		-
Inclusion/exclusion criteria	X	-	-	-	-	-		-
Complete medical history	X	-	-	-	-	-		-
Confirm diagnosis and stage/type MM	X	-	-	-	-	-		-
Performance status (ECOG)	X	X	-	X		X		X
Concurrent therapy	X	X	-	X		X		X
Safety Assessments: Adverse event query Concomitant Medication query Vital signs/ BSA 12-lead ECG Physical examination CBC w/diff  Serum Chemistry  TSH, T 3 , T 4  Pregnancy testing and counseling  Serum Free Light Chain Serum B12, RBC Folate,  Efficacy measurements: β-2-M Protein electrophoresis (serum and urine) Quantitative immunoglobulins Immunofixation studies (serum and urine)	X X X X X X X X X X 	X X X X X 	X14	X X X X X  X X  X  X -	X 	X X X X X X X X X X X X X		X 12 X X X X X X X X X X X X X X X X X X
Skeletal survey  Dosing: Register patient into RevAssist® program Prescribe study drug¹0 Count study drug returns¹0 Dispense Diary Cards Collect Diary Cards Correlative testing	X -	X  - X	-	X  X  X  X  X		X X X X X		x x x
Bone marrow aspiration for ancillary studies Peripheral blood collection for ancillary studies	Х	$X^{14}$	$X^{14}$ $X^{14}$			X  X 	X 	
Follow-up: Survival					Х			$X^8$

Screening procedures must be done within 28 days of first cycle unless otherwise specified.

Page 9 of 86 Confidential

Starting with Cycle 1, Day 1, and all tests must be done +/- 7 business days of the treatment visit day. However, pregnancy testing must be done strictly as scheduled in footnote #4 below and in sections 6.5.1 and 6.7 without an allowance of +/- 7 days.

\* An unscheduled visit can occur at any time during the study. Source must be maintained for these unscheduled visits. The date for the visit and any data generated must be recorded on the appropriate CRF. Source documents for these unscheduled visits must also be maintained.

<sup>1 All subjects are to have the designated tests performed upon discontinuation of study drug.

<sup>2 Clinical laboratory examinations include: total protein, albumin, calcium, , glucose, total bilirubin, alkaline phosphatase, AST (SGOT), ALT (SGPT), sodium, potassium, chloride, carbon dioxide, blood urea nitrogen, creatinine, and LDH.

<sup>3 Serum TSH, (Thyroid Stimulating Hormone), T3 and T4 levels every 3 months

<sup>4 Pregnancy testing for females of child bearing potential. A female of childbearing potential (a woman of childbearing potential is a sexually mature woman who: 1) has not undergone a hysterectomy or bilateral oophorectomy or 2) who has not been postmenopausal for at least 24 consecutive months [i.e., who has had menses at any time in the preceding 24 consecutive months]). Pregnancy testing must be performed 10 to 14 days and again within 24 hours prior to prescribing lenalidomide for Cycle 1. (prescriptions must be filled within 7 days). FCBP with regular or no menstruation must have a pregnancy test weekly for the first 4 weeks and then every 28 days while on therapy (including breaks in therapy); at discontinuation of lenalidomide and at Day 28 post the last dose of lenalidomide. Females with irregular menstruation must have a pregnancy test weekly for the first 4 weeks and then every 14 days while on therapy (including breaks in therapy), at discontinuation of lenalidomide and at Day 14 and Day 28 post the last dose of lenalidomide. (see Appendix VIII: Risks of Fetal Exposure, Pregnancy Testing Guidelines and Acceptable Birth Control Methods).

<sup>5 Skeletal survey is to be performed at baseline, upon addition of corticosteroids (prednisone and / or dexamethasone), discontinuation, and when clinically indicated.

Page 10 of 86 Confidential

 Bone marrow biopsy is to be performed at baseline, after 2 cycles of single agent lenalidomide therapy, to confirm CR, at the time of addition of corticosteroids (prednisone and / or dexamethasone), discontinuation, and when clinically indicated.

-  Survival follow-up to be completed every 3 months.
- CBC with diff. is required on Day 1Cycle 1 (unless baseline done within 7 days of Day 1), then every 2 weeks for the first 4 weeks of therapy. After the first 4 weeks of therapy, if the patient required a dose reduction of lenalidomide (Revlimid®) or the addition of cytokine support due to neutropenia encountered during the previous cycle, CBC with diff. is required at least every 2 weeks during the next cycle, otherwise CBC with diff. is required at least every 4 weeks. More frequent CBCs may be obtained at the investigator's discretion. After 4/2016, laboratory testing is at the discretion of the treating physician and in accordance with lenalidomide package insert. CBC will not be collected for the purpose of the trial but could be ordered per standard practise
-  Lenalidomide must be prescribed through and in compliance with Celgene's RevAssist® Program. Prescriptions must be filled within 7 days. Drug returned from the previous cycle will be counted, recorded in the patient's CRF. Patients must be instructed to return all bottles (whether empty, partial or full) at each visit. Unused lenalidomide should be returned to the patient for disposition in accordance with the RevAssist® program. After April 2016, diaries and pill counts will not be performed.
- 11. During maintenance, patients will have laboratory testing per institutional standard of care approximately every 3 months.
- 12 After April 2016, only serious adverse events SAE will be collected.
- 13 At the initiation of study and yearly thereafter.
- 14 Ancillary bone marrow aspiration will be obtained at baseline and after 2 months of lenalidomide monotherapy. Ancillary peripheral blood samples will be obtained at baseline, after 2 months of lenalidomide monotherapy and after 2 month of addition of dexamethasone .see section 9.7.4 for details regarding ancillary studies.
- 15. Patients who complete the first 6 cycles of therapy, are on a stable dose of lenalidomide for more than 2 cycles and are responding to therapy are eligible for entering a maintenance schedule of visits where office visits will be every 3 months and monitoring will be pre institutional standard of care Patient will continue to be followed for disease progression per standard clinical practice.

Page 11 of 86 Confidential

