# 9.5. Prior/Concomitant therapy

All concomitant therapies (prescription and non-prescription) taken 28 days prior to the start of study drug, Lenalidomide, and during the course of the study (from start of study drug until the last dose of study drug) will be collected. All therapies taken while the subject is on study drug will be recorded in the subject's data collection system. After April 2016, concomitant therapy will not be collected

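### No progression assessment is scheduled after the off-study visit for patients who stop lenalidomide without progression, so their 12-month primary endpoint status is not collected by plan

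*Combined protocol and SAP*

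**What the plan says.** **Follow-up after stopping.** In section 2 (Schedule of Study Assessments), footnote 1 reads: "All subjects are to have the designated tests performed upon discontinuation of study drug". After that, the Off Study column carries one recurring item, under footnote 8: "Survival follow-up to be completed every 3 months".

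**Who stops.** Section 8.1.7 lists reasons other than progression, among them adverse events, patient decision, protocol violation and "Discontinuation of lenalidomide for any reason". Several rows of Table 2 also end treatment for toxicity.

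**Other therapy.** Section 9.5 collects concomitant therapies "from start of study drug until the last dose of study drug) will be collected". An anti-myeloma treatment begun after that date is therefore outside the planned record.

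**Primary analysis.** Section 12.2.1 defines PFS as "the time from start of lenalidomide monotherapy to the first occurrence of disease progression or death on study from any cause". It then states: "All treated patients will be included in efficacy endpoint analysis". The primary statistic is a count: "Number and percentage of patients who survived greater or equal to 365 days without disease progression will be summarized". Its interval is specified as follows: "The 95% confidence interval will be calculated using the exact binominal method". The same section censors patients without an event at last follow-up and adds Kaplan-Meier curves. It does not say how a patient censored before day 365 enters the count.

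**The concern.** A binomial proportion at 365 days needs a known status for every patient in the denominator. The schedule supplies it while lenalidomide continues, but not for a living patient who stopped in month 4 because of toxicity. An analysis rule can decide how that patient is handled, but it cannot recover a status that nobody was asked to record.

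The loss is plausibly informative, because these patients have lost their treatment as well as their follow-up. They are also the patients in whom the tolerability rationale of sections 4.2.6 and 6.2 is tested. Section 6.2 intends the result to be compared with lenalidomide plus low dose dexamethasone, for which section 12.1 takes a 12-month PFS of about 70%. How a few unknown patients are handled could change how that comparison reads.

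**Working it through.** **1. The plan's own figure.** Section 12.1 gives 60 evaluable patients, an expected 12-month PFS of 85% and a 95% interval of 73.4–92.9%. The exact (Clopper-Pearson) interval for 51/60 is 73.4–92.9%, which matches; a Wald interval would be 76.0–94.0%. The planned precision thus presumes 60 known statuses.

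**2. Does any other text fill the gap?**
- Section 8.1.5 follows patients stopped for an adverse event until that event resolves or stabilizes, not for progression.
- Footnote 15 of the schedule mentions continued follow-up for progression, but for responders past six cycles on a stable lenalidomide dose.
- Section 9.7.4.1 sets response assessment at least every 3 months for the maintenance setting.
- Section 9.5 stops at the last dose.

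None of these reaches a patient who has stopped lenalidomide without progression.

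**3. Size, as proportions.** The documents state no early-stop rate, so these inputs are assumptions: a fraction q = 0.10 to 0.20 stops before day 365 without progression, 12-month PFS is 0.85 in those who stay, and stoppers' own 12-month PFS is r = 0.50 to 0.85.
- Literal count, stoppers not credited: (1 − q) × 0.85.
- Stoppers excluded: 0.85. Censoring gives about the same, slightly higher because stoppers add event-free time before they stop.
- True value: (1 − q) × 0.85 + q × r.
- Error of exclusion: q × (0.85 − r). Error of the literal count: q × r.

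| q | Literal count | Excluded | True value | Error, excluded | Error, literal |
|---|---|---|---|---|---|
| 0.10 | 76.5% | 85% | 81.5–85% | 0–3.5 points too high | 5–8.5 points too low |
| 0.20 | 68% | 85% | 78–85% | 0–7 points too high | 10–17 points too low |

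For q = 0.20: 0.80 × 0.85 = 0.68. Adding 0.20 × 0.50 gives 0.78, and adding 0.20 × 0.85 gives 0.85.

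**4. Size, in whole patients.** Here m of 60 have unknown status and about 85% of the rest are progression-free. Exact 95% intervals are in brackets.

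| m | Counted as failures | Excluded | Counted as progression-free |
|---|---|---|---|
| 3 | 48/60 = 80.0% (67.7–89.2) | 48/57 = 84.2% (72.1–92.5) | 51/60 = 85.0% (73.4–92.9) |
| 6 | 46/60 = 76.7% (64.0–86.6) | 46/54 = 85.2% (72.9–93.4) | 52/60 = 86.7% (75.4–94.1) |
| 12 | 41/60 = 68.3% (55.0–79.7) | 41/48 = 85.4% (72.2–93.9) | 53/60 = 88.3% (77.4–95.2) |

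With three unknown patients, the handling already decides whether the lower limit lies below or above 70%.

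**The case against.** The strongest objections, and what remains of each:

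- **Status is not wholly unknown.** Disease is tested at discontinuation, deaths are found through survival contact, and unscheduled visits are recorded. This stands. A reader might infer that progression is never measured in these patients. The documents support only that nothing is scheduled after the off-study visit, and routine care may well produce results.
- **The schedule table is damaged in the text available.** Footnote 7 is missing and some rows are broken, so blank cells prove little. This is fair. The point therefore rests on legible footnotes 1 and 8 and on sections 8.1.5, 9.5 and 9.7.4.1. If the intact table or footnote 7 schedules disease assessment after stopping, the point falls.
- **The plan censors, so 68% is not its rule.** This stands in part. Nothing explicitly labels stoppers as failures, and exclusion or censoring errs by only 0–7 points on these assumptions, less than the 11.6 points between 85% and the plan's lower limit of 73.4%. But the primary statistic is a count over all treated patients, and read literally it does not credit anyone censored before day 365.
- **The affected group is narrower than all who stop.** This stands. Section 6.1 replaces non-progression stops before one full cycle, although 12.2.1 analyses all treated patients. Those who withdraw consent or are lost cannot be reached by any schedule.
- **The endpoint itself is unsettled.** Sections 1 and 5 run it to the point where lenalidomide plus low dose dexamethasone fails, and 12.2.1 limits deaths to those on study. Whether progression after a toxicity stop counts is therefore unclear. This must be settled along with the data collection.
- **It is late.** Moffitt enrolment ended in 6/2013, so those 12-month windows closed by about 6/2014, before Version 6 of 4/15/2016. A schedule change cannot help there, but record review can.

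**Conclusion.** The gap is real. For consenting patients who stop lenalidomide after cycle 1 without progression, the plan schedules nothing that would establish progression status at 12 months, yet the sole primary estimate requires it. This should be corrected before the final analysis.

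Its size depends on a stopping rate that the documents do not give. At 10–20% stopping, with 85% PFS in those who stay and 50–85% in those who stop, exclusion or censoring overstates the 12-month rate by 0–7 points, and the literal count understates it by 5–17. The top of each range needs 20% stopping, with stoppers' PFS at 50% for the 7 points and 85% for the 17.

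Two stronger conclusions are not supported. The spread from 68% to 85% is not the bias of the planned estimate; it is the distance between two handling rules, and 12.2.1 does not clearly choose between them. Nor did the reduced data collection from April 2016 cause the gap at Moffitt, because the 12-month windows there had already closed.

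**What to change.** 1. **Schedule and case report form.** Amend footnote 8 and the Off Study column so that, after a stop without progression, the existing 3-monthly contact also records progression status, available paraprotein and light chain results from routine care, and the name and start date of any new anti-myeloma therapy. Continue until progression, death or at least 12 months from lenalidomide start.
2. **Closed windows.** For patients already past 12 months, which includes all Moffitt patients, abstract the same items from medical records where consent allows, before the final analysis. The documents do not give the accrual status of the South Korean sites, so check which route applies there.
3. **Section 12.2.1.** State that progression or death after stopping lenalidomide counts toward 12-month PFS. Reconcile this with the endpoint wording in sections 1 and 5 and with the restriction to deaths on study. Estimate the 12-month rate by Kaplan-Meier, and show any remaining unknown status as failure in a sensitivity analysis.

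The cost is wording, a few data fields and some results from outside laboratories, with no new visit interval. Patients who withdraw consent or are lost will remain unknown, which is why the sensitivity analysis is still needed.
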